5.3. Strategies for Recruitment and Retention

5.3.1. Community information

The community in which the study will take place will be informed about the nature and design of the study. Community leaders (chiefs, local village elders, and opinion leaders) and local health authorities

will be formally briefed in their own language on the nature and purpose of the study. They will have the opportunity to ask questions of the PI or his designees.

5.3.2. Recruitment

Adults age 18 to 55 years will be recruited from the villages in the Kombewa Health and Demographics Surveillance System (HDSS) consisting of half of Kisumu West and all of Seme Sub-Counties of Kisumu County, Kenya. Potential participants identified from within the HDSS will be approached in the community using a recruitment script by study staff delegated to carry out recruitment. Informed consent will be obtained in accordance with section 13.3. Language and illiteracy will not be impediments in the recruitment process, all briefings and explanations will be in the understandable language of the participant. It is expected that approximately 1240 adult volunteers will have to be screened to achieve the 619 subject enrolment number. HIV-infected participants will be allowed to participate in this trial, assuming they meet all eligibility criteria (less than stage 3 HIV and in the opinion of the PI they are healthy enough to participate). The study is not seeking to actively enroll HIV-positive individuals. However, given the fact that the study area has a high prevalence of HIV, it is expected that there will be HIV-positive individuals in the screening population. Therefore, the screening for HIV and staging will ensure that only healthy HIV-positive individuals are included in the study. The proportion of HIV-positive subjects enrolled in the trial is intended to reflect the same proportionate make-up of HIV-positives in the recruitment catchment areas, estimated to be approximately 15%. As such, we intend to cap HIV-positive enrollees at approximately 20-25% to avoid an over-representation by HIV-positive subjects. Final determination for enrolment of HIV-positive subjects will be determined by the Principal Investigator.

5.4. Participant Withdrawal or Termination

5.4.1. Reasons for Withdrawal or Termination

Subjects can leave the study at any time for any reason if they wish to do so without any penalty or loss of benefits to which they are otherwise entitled. Subjects can also be withdrawn from the study procedures at the discretion of the clinical investigator. The following reasons may lead to withdrawal of individual subjects:

- Withdrawal of informed consent by volunteer;
- Any serious adverse event;
- Any adverse event that, according to clinical judgment of the investigator, is considered as a definite contraindication to proceeding with the study procedures;
- Completely lost to follow-up (unable to contact after at least 3 phone or physical attempts by the study staff to locate the participant and 1 in-person attempt by a field supervisor to contact the individual; additional attempts may be made at the discretion of the PI);
- Pregnancy during immunization phase
- Ineligibility (arising during the study or retrospectively, having been overlooked at screening);
- If the investigator or DoD Research Monitor believes that continuation would be detrimental to the subject's well-being;
- Volunteer non-compliance with study requirements;
- Any other protocol deviation that results in a significant risk to the subject's safety.

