7. STUDY PROCEDURES

7.1. Study procedures and evaluations

7.1.1. Study specific procedures

This is a Phase 2b, single-center, open label, randomized controlled trial with five groups in one study site. 619 adults will be enrolled. It is assumed that 90% will complete study procedures and be evaluable. Prior to study start, a community information program will inform the local population of the study and study information will be presented at community centers. Screening procedure timelines for any single subject will include a 12-day window period before randomization. Data collection will be by CRF. Following the Screening Phase, trial-specific procedures are sub-divided into 3 separate Epochs. Epoch 1 describes the procedures during the Treatment and Immunization Phase (Appendix B). Epoch 2 describes the procedures during the Active Detection of Infection Phase (Appendix C). If insufficient number of PCR-positive events to meet both the primary and secondary endpoints occur during Epoch 2, it will be necessary to extend the ADI for an additional 24 weeks (Epoch 3, Extension Phase, Appendix D) (refer to Statistical Section 10).

A. Study-specific Screening Procedures (Appendix A)

Screening procedures are to be completed as shown in Appendix A. Screening (day -39 to day -28) may be done on a separate visit from recruiting. Only adults aged 18 to 55 years with a signed/thumb printed and dated Informed Consent document will be eligible to be screened for the trial. At the screening visit each subject will be given a Subject Screening Number (only to be used for screening) and each will have a clinic record prepared.

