10.3.4. According to protocol (ATP) cohort for efficacy

The ATP cohort for efficacy will include all subjects included in the TVC with no major protocol deviations that are determined to potentially interfere with the efficacy assessment of the study vaccine and contributed to the time at risk starting 14 days after the third dose. The membership in this study population will be determined in a blinded fashion at a data review meeting attended by the sponsor Medical Officer, the site PI/Co-PI, and the sponsor Statistician, and the list of criteria used to exclude subjects from the ATP cohort for efficacy, including vaccine or anti-malarial administration and other relevant analysis protocol deviations, will be finalized before database freeze.

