10.3.6. Total cohort for efficacy

The total cohort for efficacy includes all TVC subjects who receive all three doses of RTS,S/AS01_E vaccine or comparator and contributed to the time at risk starting 14 days after the third dose.

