participant and the study staff conducting informed consent explanation will sign and date the consent form. The participant signature confirms that (s)he has understood the information. For illiterate individuals, the informed consent process will be conducted in the presence of a literate impartial witness selected by the participant but not a member of the KCRC staff. The participant will thumb print the consent form and the witness will write the participant's name, sign and date the consent form. Each volunteer's consent form will be kept in their study folder and a copy will be given to the participant to take home on the same day. In case of any amendments to the protocol resulting in changes in study procedures, the participant will be informed and additional informed consent will be obtained if necessary. In accordance with Good Clinical Practice, the volunteer may terminate participation in the study at any time for any reason without penalty. Additionally, if the participant is unable or unwilling to adhere to the protocol design, the investigator may terminate volunteer's participation. The study team will use the participant's preferred language usually English, Kiswahili or Luo for informed consent.

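### Investigator withdrawal for non-compliance or late-found ineligibility ends PCR follow-up in an open-label trial, and neither efficacy cohort can show the resulting bias

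*Protocol*

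**What the plan says.** Section 7.1.1 describes the design: "This is a Phase 2b, single-center, open label, randomized controlled trial with five groups in one study site". Section 5.4.1 gives the investigator discretion: "Subjects can also be withdrawn from the study procedures at the discretion of the clinical investigator". The reasons that may lead to withdrawal include "Volunteer non-compliance with study requirements", with no threshold, and "Ineligibility (arising during the study or retrospectively, having been overlooked at screening". Section 13.3.2 restates the power: "if the participant is unable or unwilling to adhere to the protocol design, the investigator may terminate volunteer's participation".

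Three sections govern what follows:
- Section 5.4.2 keeps following subjects withdrawn because of an AE or SAE until the event settles, and pregnant subjects for safety. It provides nothing for other withdrawals.
- Section 7.1.1 part E gives the Study Termination Visit only to participants who have not been withdrawn.
- Section 10.4.5 leaves discontinued participants out of analyses beyond the time of discontinuation.

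The primary and secondary efficacy analyses are Cox models in the ATP cohort for efficacy (10.4.2, 10.4.3). On that cohort, 10.3.4 says: "The membership in this study population will be determined in a blinded fashion at a data review meeting". The total cohort for efficacy (10.3.6) takes subjects who received all three doses and who "contributed to the time at risk starting 14 days after the third dose".

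**The concern.** The protocol already has a place to deal with deviators: the review under 10.3.4, with 10.3.6 as the wider set that retains three-dose subjects whom the ATP cohort drops. Withdrawal by the investigator bypasses both. It is decided earlier, at the single site, with the vaccine known. The site may also know things that predict infection: clinical malaria found in Epoch 1 is recorded in the CRF although it is not an endpoint (7.1.1 part B).

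A Cox model needs censoring that is unrelated to the outcome given group. If these withdrawals track infection risk differently in the two groups, the hazard ratio is biased. Because the same person-time is missing from both efficacy cohorts, agreement between them would say nothing about this particular source of bias. PCR samples that were never taken cannot be recovered by any later analysis plan.

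**Working it through.** **1. What happens to a withdrawn subject in Groups 1, 2, 4 or 5**

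| Situation | ATP cohort (10.3.4) | Total cohort (10.3.6) |
|---|---|---|
| Major deviation, not withdrawn, three doses, time at risk | may be excluded | stays in |
| Withdrawn by the investigator during ADI | counts at most up to withdrawal | counts up to withdrawal only |
| Withdrawn before dose 3 | not in | not in |

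The total cohort adds information in the first row only. Group 3 has no efficacy endpoint and is not affected.

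**2. Reproducing the plan's figures (10.5)**

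Inputs: 164 per group in Groups 1 and 4, 10% dropout, 40% attack rate over 6 months, vaccine efficacy (VE) 50%, so hazard ratio (HR) 0.5.
- Evaluable per group: 164 × 0.9 = 147.6.
- RTS,S risk: 1 − 0.6^0.5 = 0.2254.
- Expected events: 147.6 × 0.2254 = 33.3 and 147.6 × 0.40 = 59.0, total 92.3. The plan states 92.
- For Groups 2 and 5: 128 × 0.9 = 115.2, and 115.2 × (0.2254 + 0.40) = 72.0. The plan states 72.

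The sample size stands. The point concerns bias, not power.

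**3. Illustration of selective loss, Groups 1 and 4**

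The protocol gives no number of investigator withdrawals and no risk for those withdrawn, so both are assumptions here. Remove k subjects with risk r from one group at the start of ADI:

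p = (events − k·r) / (147.6 − k) in that group, and VE = 1 − ln(1 − p_RTS,S) / ln(1 − p_rabies).

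For k = 5 in the RTS,S group, with ln(0.6) = −0.5108:
- r = 0.2254 (unrelated to risk): p stays 0.2254 and VE = 50%.
- r = 0.4508 (double the planned risk): p = (33.27 − 2.25) / 142.6 = 0.2175; ln(0.7825) = −0.2453; VE = 1 − 0.2453/0.5108 = 52.0%.
- r = 1 (all would have been infected): p = 28.27 / 142.6 = 0.1982; ln(0.8018) = −0.2210; VE = 56.7%.

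| Subjects lost | RTS,S group, double risk | RTS,S group, r = 1 | Rabies group, r = 1 |
|---|---|---|---|
| 3 | 51.2% | 54.0% | 47.9% |
| 5 | 52.0% | 56.7% | 46.4% |
| 7 | 52.8% | 59.5% | 44.7% |

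**4. The same idea with no true effect**

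Take 164 per group, a 40% risk in both, and 8 lost from Group 1 only. With r = 0.40 the apparent VE is 0% and the one-sided type I error is 0.025. With r = 1 the remaining risk is (65.6 − 8)/156 = 0.369, HR = ln(0.631)/ln(0.6) = 0.90, apparent VE is about 10%, and the one-sided type I error is about 0.083 (normal approximation on the log hazard ratio, 123.2 events, standard error √(4/123.2) = 0.18).

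**The case against.** Much of the other side's case stands.

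- Withdrawal is permitted, not required. Missed antimalarial doses (7.1.1 part B) and out-of-window visits (7.3) are handled as deviations and do not in themselves trigger withdrawal. The last item in 5.4.1, on other deviations, is limited to those carrying a significant safety risk.
- The protocol does not always merge stopping product with leaving. Section 8.4.4 stops further vaccine doses in pregnancy but allows other study procedures to continue.
- A reader might infer that the total cohort is useless as a check on the ATP result. The documents do not support that: it keeps three-dose deviators who were not withdrawn. Nor do subjects withdrawn during ADI vanish from it, since their time and any event before withdrawal count.
- A reader might take 57% or 60% as the expected distortion. Those figures need every removed subject to be a certain future infection, all in one group and all lost at the start. The first positive PCR in ADI is already the event, so later withdrawal cannot erase it, and a symptomatic subject has PCR taken at that visit. At the planned RTS,S risk, losing 5 events would mean withdrawing about 22 subjects (5 / 0.2254), with no bias.
- The 10% dropout allowance covers all causes and is not a forecast of investigator withdrawals.
- Section 5.4.2 records who decided and why, so an imbalance between groups would be visible.

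That last safeguard would show an imbalance in withdrawals but would not supply the missing outcomes. Nothing cited restores PCR surveillance for a subject withdrawn for non-compliance or late-found ineligibility.

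**Conclusion.** The point holds as a limited one. Sections 5.4.1 and 13.3.2 allow withdrawal for two reasons that need not involve safety, by someone who knows the vaccine given, and 5.4.2, 7.1.1 part E and 10.4.5 provide no PCR follow-up or analysis afterwards. The total cohort for efficacy can check ATP exclusions of deviators who remained, but it cannot reveal bias from these withdrawals.

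The size is unknown. It is zero if withdrawal is unrelated to infection risk, about 2 percentage points of VE for 5 RTS,S subjects at double the planned risk, and about 7 points at the extreme. These figures rest on the planning assumptions in 10.5 and on assumed numbers and risks of those withdrawn. This is a worthwhile, inexpensive improvement; it does not show that the efficacy analyses would be invalid.

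**What to change.** In 5.4.1, 5.4.2 and 13.3.2, state that non-compliance or ineligibility found retrospectively does not by itself end the 3-weekly PCR schedule, Visit 27, the Study Termination Visit or SAE follow-up, provided the subject still consents. Align 7.1.1 part E and 10.4.5 with that wording.

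Leave unchanged withdrawal for safety or well-being (5.4.1), the Research Monitor's authority (8.5.1) and any decision to stop study product.

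Leave the exclusion of three-dose deviators to the 10.3.4 review and keep them in 10.3.6. Because 10.3.6 requires three doses, subjects stopped before dose 3 stay outside it however many samples they give; use their PCR data in a supportive analysis of the total vaccinated cohort (10.3.2).

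The cost is protocol wording and a few more finger-prick visits within the existing schedule. Event targets and sample size do not change.

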5.4.2. Handling of Participant withdrawals or termination

Investigators, or designee, will follow subjects who are withdrawn as result of a SAE/AE until resolution of the event and/or chronicity is established. Study staff will make an attempt to contact those subjects who do not return for scheduled visits or follow-up. Information relative to the withdrawal will be documented on the CRF. The investigator will document whether the decision to withdraw from the study was made by the subject or the investigator and which of the following possible reasons was responsible for withdrawal:

- serious adverse event
- non-serious adverse event
- protocol violation (specify)
- consent withdrawal, not due to an adverse event
- moved from the study area
- lost to follow-up

If a subject withdraws or is terminated from the study after enrolment and receipt of investigational product (including anti-malarial medications), including lost to follow-up, they will not be replaced. If a subject withdraws or is terminated from the study after enrolment but prior to receipt of investigational product, including lost to follow-up, (e.g., participant in group 3 who withdraws or is terminated between study visits 2 and 5) that participant may be replaced.

If the reason for withdrawal from the study is pregnancy during the immunization phase of the study, the participant will be withdrawn from any further immunizations, but will be followed for safety until delivery or termination of the pregnancy.

5.5. Premature Termination or Suspensions of Study

This study may be temporarily suspended or prematurely terminated if there is sufficient reasonable cause as determined by the sponsor, PATH. Written notification, documenting the reason for study suspension or termination, will be provided to the investigator, GSK, WRAIR IRB, and to Kenyan regulatory authorities. If the study is prematurely terminated or suspended, the PI will promptly inform the IRB and will provide the reason(s) for the termination or suspension.

6. STUDY VACCINE

6.1. Study Vaccine and Antimalarial Medications

Refer to the IB for details of the description of RTS,S/AS01_E. The IB for RTS,S and the package inserts for Abhayrab®, DHA/Pip, A/L, and Primaquine will be provided to the ethical and regulatory review committees. The candidate RTS,S/AS01 vaccine to be used has been developed and manufactured by GSK Biologicals. The vaccine is labelled and packed according to applicable regulatory requirements.

The RTS,S/AS01_E vaccine presentation is provided as a clipped two-vial combination in 3 mL vials, one vial of RTS,S antigen and a second vial of AS01_E adjuvant. RTS,S antigen is a lyophilized pellet containing

50 µg of RTS,S per vial. The pellet is reconstituted with 1mL adjuvant in liquid form and 0.5 mL dose of reconstituted vaccine contains 25 µg RTS,S. The AS01_E adjuvant contains 25 µg of MPL®, 25 µg QS21 (QS21 is a triterpene glycoside purified from the bark of *Quillaja saponaria*) in a suspension of liposomes in phosphate buffered saline per 0.5 mL and is presented in 3 mL vials. A dose of 0.5 mL (first two immunizations) or 0.1 mL (third immunization) will be delivered as appropriate. The presentation of the reconstituted RTS,S/AS01_E candidate malaria vaccine is an opalescent liquid.

Table 4. Vaccine Formulation and Presentation

Treatment name	Vaccine/product name	Formulation	Presentation	Volume to be administered
RTS,S/AS01 _E (Full dose)	RTS,S	RTS,S=25µg	Lyophilized pellet in a glass vial	0.5 mL
	AS01 _E	MPL=25µg; QS21=25µg; Liposomes	Liquid solution in a glass vial	
RTS,S/AS01 _E (1/5 th dose)	RTS,S	RTS,S=5µg	Lyophilized pellet in a glass vial	0.1 mL
	AS01 _E	MPL=5µg; QS21=5µg; Liposomes	Liquid solution in a glass vial	
Rabies vaccine	Abhayrab	Rabies virus = 2.5 IU	Powder and solvent for solution for injection. After dissolution of the white lyophilizate (powder), a clear colorless solution is obtained.	0.5 mL

The Abhayrab vaccine is a sterile freeze-dried vaccine obtained by growing the fixed-virus strain Flury LEP in primary cultures of chicken fibroblasts. The potency of one dose (0.5 mL) Abhayrab is at least 2.5 IU of rabies antigen. Abhayrab is a white, freeze-dried vaccine for reconstitution with the diluent prior to use; the reconstituted vaccine is a clear to slightly opaque, colorless suspension. A dose of 0.5 mL will be delivered. The presentation of the reconstituted vaccine is as a clear or slightly opaque suspension.

6.1.1. Acquisition

RTS,S/AS01_E will be provided by GSK and sent directly to the study site in Kisumu, Kenya. Abhayrab, DHA/Pip, Coartem®, and Primaquine will be procured by USAMRD-A.

6.1.2. Formulation, Appearance, Packaging, and Labeling

See IB and package inserts for details.

6.1.3. Product Storage and Handling

All vaccine vials (RTS,S/AS01_E and Abhayrab rabies vaccines) must be stored in the refrigerator (+2°C to +8°C) and must not be frozen. All vaccine/adjuvant/water for injection vials will be stored in a safe and locked place with no access for unauthorized personnel. The storage conditions will be assessed during pre-study activities under the responsibility of the sponsor study contact. The storage temperature should be continuously monitored with calibrated (if not validated) temperature monitoring device(s) and recorded according to SOPs at the investigator's site. An alarm system and a back-up refrigerator will be available in case of power failure/breakdown. Whether it occurs prior to receipt of RTS,S vaccine at site or after, GSK and the study monitor must be contacted if the cold chain is broken (e.g. vaccines become frozen or refrigeration fails).

GSK will manage temperature deviations during the primary shipment until the reception at the clinical trial site. Temperature excursions are the responsibility of PATH upon receipt of RTS,S/AS01 study product. Data will be provided to PATH that will allow PATH to decide whether the IP can still be administered or should be destroyed following a temperature excursion. Any temperature excursion outside the range of 0.0 to +8.0°C (for +2 to +8°C/+36 to +46°F label storage condition) impacting investigational medicinal products (IMPs) must be reported to PATH. In case of temperature excursion below +2.0°C down to 0.0°C impacting IMP(s) there is no need to report, but adequate actions must be taken to restore the +2 to +8°C/+36 to +46°F label storage temperature conditions. The impacted IMP(s) may still be administered, but the site should avoid re-occurrence of such temperature excursion.

All anti-malarial medications should be stored below 30°C.

6.1.4. Preparation

In this study, the RTS,S/AS01_E will be supplied in clipped vials, i.e. a two-dose glass vial of lyophilized RTS,S antigen (50 µg) to be reconstituted with a two-dose glass vial of AS01_E Adjuvant System (1.0 ml). The final product for administration will be prepared by reconstitution of the lyophilized antigen with the liquid adjuvant. From the reconstituted vaccine vial, 0.5 mL will be administered for RTS,S/AS01_E full doses or 0.1 mL will be administered for RTS,S/AS01_E fractional doses (1/5th dose). All vials of vaccine provided in this study are intended for single use only.

6.1.5. Dosing and Administration

Refer to dosing and administration of DHA/Pip, Coartem®, and Primaquine in Table 5.

Table 5. Anti-malarial Medications

Study Agents	Dosage forms and strength	Body weight	Day 1 (AM)	Day 1 (+8hr)	Day 2 (AM)	Day 2 (PM)	Day 3 (AM)	Day 3 (PM)
Dihydroartemisinin-piperaquine	Dihydroartemisinin (40 mg) and piperaquine tetraphosphate (320 mg)	36 to <75 kg	3 tabs	-	3 tabs	-	3 tabs	-
		75 to 100 kg	4 tabs	-	4 tabs	-	4 tabs	-
COARTEM **	artemether (20 mg) and lumefantrine (120 mg)	> 35 kg	4 tabs	4 tabs @ 8 hrs	4 tabs	4 tabs	4 tabs	4 tabs

PRIMAQUINE***	primaquine phosphate tablets 26.3 mg primaquine phosphate (equivalent to 15 mg primaquine base)	> 35 kg	1 tab	-	-	-	-	-	-
---------------	---	---------	-------	---	---	---	---	---	---

*Dihydroartemisin-piperaquine should be taken at approximately the same time each day – refer to the Manual of Operating Procedures for further details. Dihydroartemisin-piperaquine should be taken orally with water. No food should be taken within 3 hours before and after each dose.

** Coartem should be taken with food

***Primaquine may be taken with food

